14.6 Other Safety Endpoints

There are no other safety endpoints in this study.

15. CLINICAL PHARMACOKINETIC AND PHARMACODYNAMIC ANALYSES

For trofinetide-treated subjects, whole blood concentration for trofinetide will be listed. Whole blood concentration data for trofinetide will be summarized for the PK Analysis Set at each visit using descriptive statistics. Concentrations that are below the limit of quantification (BLQ) will be displayed as “BLQ” in the data listings and imputed as 0 for computing summary statistics.

If data allow, population PK and PK/PD analyses will be performed to further characterize the PK profile and exposure response relationship of trofinetide using measures of safety and efficacy parameters. The results of population PK and PK/PD modeling will be presented in a separate report. Trofinetide whole blood concentration data will remain blinded until the unblinding of the clinical database at the end of the study.

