1.3 Previous Clinical Experience

Trofinetide showed linear pharmacokinetics (PK) across the dose range tested in pediatric RTT patients. These PK results are in agreement with the data obtained previously in healthy subjects and in adult RTT patients. From a drug metabolism perspective, there was no accumulation, metabolic inhibition, or induction observed during treatment. For subjects treated with 50 mg/kg twice daily (BID), median maximum (peak) observed drug concentration (C_{\max}) was 17.7 $\mu\text{g/mL}$ and median $\text{AUC}_{0-12\text{ss}}$ was 139.4 $\mu\text{g/mL}\cdot\text{h}$. For subjects treated with 100 mg/kg BID, median C_{\max} was 52.6 $\mu\text{g/mL}$ and median $\text{AUC}_{0-12\text{ss}}$ was 338.6 $\mu\text{g/mL}\cdot\text{h}$. For subjects treated with 200 mg/kg BID, median C_{\max} was 82.2 $\mu\text{g/mL}$ and median $\text{AUC}_{0-12\text{ss}}$ was 505.1 $\mu\text{g/mL}\cdot\text{h}$. The geometric mean of the apparent terminal elimination half-life ($t_{1/2}$) varied from 5.3 h to 6.1 h across the three dosing groups.

Trofinetide has exhibited a favorable safety and tolerability profile in two studies in subjects with Rett syndrome. Study Neu-2566-Rett-001 (NCT01703533) was a Phase 2 study of trofinetide in 56 adolescent and adult females with RTT (Glaze et al. 2017). Subjects were randomized 2:1 to 35 mg/kg trofinetide BID or placebo for 14 or 28 days (Cohorts 0 and 1, respectively) or 70 mg/kg trofinetide BID or placebo for 28 days (Cohort 2). Both dose levels were well-tolerated in this study, and no time- or dose-dependent adverse events (AEs) were apparent. The most common AE across all treatment groups was diarrhea (39% in the combined 35 mg/kg BID group, 11% in the 70 mg/kg BID group and 15% in the placebo group). The most common AE in the 70 mg/kg BID group was somnolence (17%; vs. 5% in the placebo group and 0% in the 35 mg/kg BID group). Four serious adverse events (SAEs) involving three subjects were reported during the study. In each of these instances, the AEs were deemed unrelated to the study medication. One subject withdrew from the study due to these events while the two subjects had already finished the study medication when their SAEs occurred. Each of these SAEs was deemed to be resolved by study conclusion. The results of this study also provided preliminary evidence of a treatment effect in the 70 mg/kg BID treatment group.

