6.4 Pharmacokinetic Assessments

Pharmacokinetic blood samples will be collected for measurement of whole blood concentrations of trofinetide and any relevant possible metabolites identified.

Pharmacokinetic blood samples will be collected for trofinetide concentration measurements at the Baseline visit (both before dosing and after dosing) and at Visit 2, Visit 3, Visit 4, and Visit 5 in accordance with the sampling schedule outlined below ([Table 6-1](#)).

The PK sample taken at the Week 12/EOT visit in the antecedent study is the predose PK blood sample for the present study. The second PK sample to be taken at the Baseline visit (Visit 1), approximately 2-3 hours after dosing, will take place as soon as possible after the postdose ECG is performed.

PK samples at Visits 2, 3, 4, and 5 will be collected at one of the following time intervals:

- 2-3 hours after dosing
- 4-6 hours after dosing
- 7-11 hours after dosing

Every effort should be made to collect PK samples at discrete time intervals during Visits 2, 3, 4, and 5. However, if the interval is the same at each visit, then the collection time should

vary within that interval. The following scenario is only for illustrative purposes, a number of other scenarios are possible.

- For example, if the time interval of 4-6 hours after dosing is used for Visit 2, 3, 4, and 5, then every effort should be made to collect PK samples at 4, 4.5, 5, and 6 hours after dosing, respectively.

Pharmacokinetic samples will also be collected, if possible, at any ET visit or the visit immediately following any SAE or following any AE leading to discontinuation, even if it is an unscheduled visit.

For all scheduled PK samples (and for unscheduled samples if possible), the dates and times of administration of the study drug, the dates, times and content of the meals, and the dates and times of the administration of concomitant medication over the 2 days prior to and on the morning of the PK sample draw, as well as the date and time of the sample draw, will be recorded. For samples collected from subjects who experience any SAE or experience an AE leading to discontinuation, the date and time of the last dose of study drug prior to the SAE or AE leading to discontinuation will also be recorded.

Table 6-1 PK Sampling Times

Visit	Timing of Sample (relative to start of dosing on the visit day)	Week of Treatment
1 (Baseline)	Any time before dosing and 2 – 3 hours after dosing (after ECG)	Week 0 (Baseline)

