5.5 Analysis Visit Windows

Efficacy, safety, and PK assessments will be summarized by analysis visit as presented in Table 2 below.

Table 2 Analysis Visit Windows

| Analysis Visit | Target Study Day | Study Day Interval |
|------------------------|------------------|--------------------|
| Baseline (Day 1) | 1 | ≤ 1 |
| Day 1 Post First Dose* | 1 | 1 |
| Week 2 | 15 | 2 – 49 |
| Week 12 | 85 | 50 – 133 |
| Week 26 | 183 | 134 – 231 |
| Week 40 | 281 | 232 – 310 |

*For ECG and PK assessments only; other assessments post-first dose on Day 1 will go to the Week 2 analysis visit window.

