5.5.1 Unscheduled Assessments

Both Scheduled and Unscheduled assessments, including the assessments at early termination visits, will be included for planned timepoint analyses based on the above analysis visit windowing rules. All assessments will be presented in data listings.

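### Trofinetide concentrations are summarized by visit only, although Visit 2–5 samples may be drawn 2–3, 4–6 or 7–11 h after dosing, so a visit mean has no defined time after dose

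*SAP*

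**What the plan says.** SAP section 15 gives the summary rule for the PK Analysis Set: "Whole blood concentration data for trofinetide will be summarized for the PK Analysis Set at each visit using descriptive statistics". SAP section 5.5 sets the time variable: "Efficacy, safety, and PK assessments will be summarized by analysis visit as presented in Table 2 below". Table 2 defines its windows in study days. The only split within a day is the row for Day 1 after the first dose, with the footnote "For ECG and PK assessments only; other assessments post-first dose on Day 1 will go to the Week 2 analysis visit window". SAP section 5.5.1 adds: "Both Scheduled and Unscheduled assessments, including the assessments at early termination visits, will be included for planned timepoint analyses".

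Protocol section 6.4 governs the draws: "PK samples at Visits 2, 3, 4, and 5 will be collected at one of the following time intervals", namely 2–3, 4–6 or 7–11 h. It continues: "Every effort should be made to collect PK samples at discrete time intervals during Visits 2, 3, 4, and 5". It sets no order of intervals and no balance between them. If one interval is used throughout, times should vary inside it, and the illustration for 4–6 h is that "every effort should be made to collect PK samples at 4, 4.5, 5, and 6 hours after dosing, respectively". The Day 1 post-dose sample is fixed at about 2–3 h. Times of doses and draws are recorded.

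Protocol section 9.5.4 asks only for listing and descriptive statistics. Neither document stratifies or adjusts the descriptive summary by time after dose.

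**The concern.** Whole blood concentration is a stated PK endpoint (Protocol 2.3.1), serving the objective of characterizing PK after long-term treatment. A row for Week 12, say, would average near-peak, mid-interval and late samples. Such a mean describes no particular point on the concentration curve, and its SD mixes differences between subjects with differences in sampling time. Because the table is laid out by visit, it also invites reading down the weeks, where a change in the mix of intervals would look like a change in exposure.

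**Working it through.** The documents state no numerical target for this summary, so there is no figure to reproduce.

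**Inputs.** Sampling intervals come from Protocol 6.4. The geometric mean terminal half-life "varied from 5.3 h to 6.1 h across the three dosing groups" comes from Protocol 1.3; it was measured in Phase 2 groups dosed in mg/kg and is carried over here as an assumption. The share of samples in each interval is not given, so the mixes below are assumed.

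**1. Is mono-exponential decline reasonable?** With k = ln 2 / t½, a single decline from the stated Cmax gives AUC(0–12) = (Cmax/k) × (1 − e^(−12k)).

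| Dose (mg/kg BID) | Cmax | AUC, t½ 5.3–6.1 h | AUC stated |
|---|---|---|---|
| 200 | 82.2 | 497.7–538.4 | 505.1 |
| 100 | 52.6 | 318.5–344.5 | 338.6 |
| 50 | 17.7 | 107.2–115.9 | 139.4 |

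The fit is close at the two higher doses and 17–23% low at the lowest. It is adequate for sizing.

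**2. Expected concentration by interval.** With draws spread evenly over [a, b], the mean is proportional to (e^(−ka) − e^(−kb)) / (k(b − a)). Relative to 2–3 h:

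| Interval | t½ 5.3 h | t½ 6.1 h |
|---|---|---|
| 2–3 h | 1 | 1 |
| 4–6 h | 0.723 | 0.754 |
| 7–11 h | 0.432 | 0.482 |

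**3. Spread from sampling time alone.** For an equal mix at the midpoints 2.5, 5 and 9 h, the values are 1, 0.721, 0.427 (mean 0.716, CV 33%) at 5.3 h and 1, 0.753, 0.478 (mean 0.743, CV 29%) at 6.1 h.

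**4. Change in the visit mean with constant exposure** (mixes in the order 2–3/4–6/7–11 h):

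- 40/30/30 to 30/30/40: 0.747 to 0.690 (−7.6%) at 5.3 h; 0.771 to 0.719 (−6.7%) at 6.1 h.
- 50/30/20 to 20/30/50: 0.803 to 0.633 (−21.2%) at 5.3 h; 0.823 to 0.667 (−18.9%) at 6.1 h.
- The same mix at both visits: 0%.
- The shifts reversed: about +7 to +8% and +23 to +27%.

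**5. Drift inside one interval.** The protocol's illustration of 4, 4.5, 5 and 6 h at Visits 2–5 gives 1, 0.937–0.945, 0.877–0.893 and 0.770–0.797. That is a 20–23% fall from Week 2 to Week 40 with no change in exposure.

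**6. Sensitivity to absorption.** In a one-compartment oral model at steady state with an assumed absorption rate of 0.5 per hour, the ratios are 0.92–0.94 at 4–6 h and 0.61–0.66 at 7–11 h. At 1 per hour they are 0.79–0.82 and 0.48–0.53. The illustration in step 5 then gives a fall of 12–21%. The effect shrinks with slow absorption but does not vanish.

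**7. Day 1 against later visits.** Without accumulation, the equal-mix mean is 0.716–0.743 of a 2.5 h sample, a gap of 26–28%. Under the same model with 12 h dosing (assumed), accumulation is 1/(1 − 2^(−12/t½)) = 1.26–1.34. For a subject coming from placebo, the ratio becomes 0.716 × 1.263 = 0.90 to 0.743 × 1.344 = 1.00, a gap of 0–10%.

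**The case against.** The strongest defence is that one sample per visit at varied times is a sparse design meant for a population model, which uses actual times and doses. That stands as a defence of the sampling, which is not at fault. It does not repair the descriptive table: the modelling is conditional on the data allowing it, is reported separately, and is excluded from this SAP by its section 1.

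Table specifications are in a separate document and may already split by interval. That cannot be checked here; the SAP as written does not require it.

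No comparison of concentrations between visits is planned. The change-from-baseline rule in SAP 5.1 covers safety and efficacy measures, and no testing is planned. This stands and limits the severity.

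A reader might infer that the Week 2–40 means will show a false fall in exposure. The documents do not support this. Asking each subject to vary intervals does not imply that the whole cohort drifts later, and the direction and size depend on a mix that is not given.

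A reader might also infer that later visits will sit about a quarter below Day 1. That holds only without accumulation. Protocol 1.3 reports none observed, whereas the simple model implies some for subjects coming from placebo. Day 1 is also not a common starting point: under Protocol 3.1.1, most subjects took their last antecedent dose that morning, so those previously on trofinetide may carry drug over and those on placebo do not.

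**Conclusion.** The point holds as a weakness in how the summary is specified. The rule pools intervals whose expected concentrations differ about twofold between 2–3 h and 7–11 h, assuming mono-exponential decline at the Phase 2 half-life (about 1.5- to 1.6-fold at the slowest absorption tried). That the pooled mean has no defined time after dose follows whatever the mix. An apparent trend is only a possibility, in either direction, and the percentages for it are illustrations under assumed mixes. Early-termination and unscheduled samples enter the same windows, and values below quantification are set to zero (SAP 15), so draws long after a dose could lower a mean further. Dose changes allowed during treatment (Protocol 5.1.3.2) can also move visit means. No primary endpoint or decision rule depends on the table. Severity is minor.

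**What to change.** In SAP section 15, replace the by-visit rule with the following:

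- Summarize concentrations by visit and actual post-dose interval (2–3, 4–6, 7–11 h). Give n and the median and range of actual time after dose in each cell, because timing can still drift inside an interval.
- List separately any samples outside these intervals, and early-termination or event-driven samples without a qualifying time.
- Show the Day 1 post-dose sample by antecedent treatment group, and set it only beside later 2–3 h samples of the same group.
- State that any pooled by-visit mean is not to be read as change over time, and that dose changes also affect it.

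With a constant exposure and draws spread alike within each interval, a shift in the interval mix then changes no cell mean.

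The cost is SAP wording and more table rows; the times needed are already recorded. Cells become smaller: if all 180 planned subjects gave a sample and split evenly, 180 / 3 = 60 per interval per visit, and fewer within each antecedent group.

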16. INTERIM ANALYSIS

No interim analysis is planned in this study. If a new drug application (NDA) submission happens before the completion of this study, an interim data cut will be scheduled for that purpose.

17. DATA MONITORING/REVIEW COMMITTEE

Data from this study will be reviewed by the Data and Safety Monitoring Board (DSMB) for study ACP-2566-003.

18. COMPUTER METHODS

Statistical analyses will be performed using Version 9.4 (or newer) of SAS® on a qualified and validated environment.

Validation and quality control of the tables, listings and figures containing the results of the statistical analyses will follow appropriate standard operating procedures.

19. CHANGES TO ANALYSES SPECIFIED IN PROTOCOL

No changes are made to the analyses specified in the protocol.

21. APPENDICES

21.1 Schedule of Assessments

| Period | Baseline | Open-label Treatment Period | | | | Safety Follow-up ^k |
|---|--------------------|-----------------------------|----------------|----------------|----------------|-------------------------------|
| | | 2 | 12 | 26 | 40/EOT/ET | |
| Visit Week | 0 | 2 | 12 | 26 | 40/EOT/ET | EOT/ET+ 30 days |
| Visit Number | 1 | 2 | 3 | 4 | 5 | |
| Visit window (days) | N/A | ±3 | ±7 | ±7 | +7 | +4 |
| Type of Visit ^l | Clinic or Off-site | | | | | Telephone or Telemedicine |
| Informed consent | X ^a | | | | X ^a | |
| Inclusion/exclusion criteria | X | | | | | |
| Medical history update | X | | | | | |
| Physical examination ^l | X | X | X | X | X | |
| Vital signs ^b | X | X | X | X | X | |
| Height | X | | | | X | |
| Weight ^l | X ^l | X | X | X | X | |
| 12-lead electrocardiogram (ECG) ^e | X ^c | X | X | X | X ^c | |
| Clinical laboratory tests (hematology, chemistry) ^m | X | X | X | X | X | |
| Urinalysis | X | X | X | X | X | |
| TSH, Free T3, Free T4 | X | | | | X | |
| Serum pregnancy test ^d | X | | X | X | X | |
| Blood samples for pharmacokinetics | X ^e | X ^f | X ^f | X ^f | X ^f | |
| Blood sample for optional analysis for biomarkers ^g | X ^h | | X | X | X | |
| Rett Syndrome Behaviour Questionnaire (RSBQ) | X | X | X | X | X | |
| Clinical Global Impression–Improvement (CGI-I) ⁱ | | X | X | X | X | |
| Clinical Global Impression–Severity (CGI-S) | X | X | X | X | X | |
| Communication and Symbolic Behavior Scales-Developmental Profile™ Infant-Toddler (CSBS-DP-IT) Checklist | X | X | X | X | X | |

21.1 Schedule of Assessments (Continued)

| Period | Baseline | Open-label Treatment Period | | | | | Safety Follow-up ^k |
|--|--------------------|-----------------------------|----|----|----|-----------|-------------------------------|
| | | 0 | 2 | 12 | 26 | 40/EOT/ET | |
| Visit Week | 1 | 2 | 3 | 4 | 5 | | EOT/ET+ 30 days |
| Visit Number | N/A | ±3 | ±7 | ±7 | +7 | | +4 |
| Type of Visit ^l | Clinic or Off-site | | | | | | Telephone or Telemedicine |
| Impact of Childhood Neurologic Disability Scale (ICND) | X | | | | | X | |
| Rett Syndrome Clinician Rating of Hand Function (RTT-HF) | X | X | X | X | X | | |
| Rett Syndrome Clinician Rating of Ambulation and Gross Motor Skills (RTT-AMB) | X | X | X | X | X | | |
| Rett Syndrome Clinician Rating of Ability to Communicate Choices (RTT-COMC) ^l | X | X | X | X | X | | |
| Rett Syndrome Clinician Rating of Verbal Communication (RTT-VCOM) | X | X | X | X | X | | |
| Rett Syndrome Caregiver Burden Inventory (RTT-CBI) | X | | X | | X | | |
| Dispensing and review of semi-structured caregiver diary | X | X | X | X | X | | |
| Concomitant medications | X | X | X | X | X | | X |
| Assessment of adverse events | X | X | X | X | X | | X |
| Study drug dispensed ^j | X | | | | | | |
| Authorization of study drug dispensation ^j | X-----X | | | | | | |
| Study drug return ^j | | X-----X | | | | | |
| Study drug accountability ^j | | X | X | X | X | | |

Abbreviations: EOT=end of treatment; ET=early termination

a Unless subjects are enrolling in the present study under special circumstances due to the COVID-19 public health emergency (detailed in the inclusion/exclusion criteria), consent for the present study must be obtained prior to performance of the EOT procedures at the Week 12/EOT visit in the antecedent study. Data from the Week 12/EOT visit procedures of the antecedent study will be carried over as Baseline information in the present study, as applicable. Subjects who enter the present study under special circumstances due to the COVID-19 public health emergency will have consent obtained for the present study before any procedures are performed (e.g., the blood draw before the

Baseline visit). For subjects who decide to continue into subsequent open-label extension (OLE) study (ACP-2566-005), informed consent for ACP-2566-005 must be obtained prior to performing the Week 40/EOT procedures.

- b Vital signs will include body temperature, resting respiration rate, sitting systolic and diastolic blood pressure, and pulse rate. The sitting blood pressure will be measured after the subject has been sitting for ≥ 3 minutes.
- c ECGs will be completed in triplicate at Visit 1 (Baseline) both before dosing and 2-3 hours after dosing and at Visit 5 (Week 40/EOT/ET). For those subjects who completed the antecedent study, the ECG taken at the Week 12/EOT visit in the antecedent study is the predose Baseline ECG of the present study. A single ECG will be completed at Visit 2 (Week 2), Visit 3 (Week 12), and Visit 4 (Week 26).
- d For subjects who have reached menarche and have not had surgical sterilization
- e The PK sample taken at the Week 12/EOT visit in the antecedent study is the predose PK blood sample for the present study. A postdose PK blood sample will be collected at the end of ECG assessment 2-3 hours after the first dose of study drug in the present study.
- f PK samples at Visits 2, 3, 4, and 5 will be collected at one of the following time intervals: 1) 2-3 hours after dosing OR 2) 4-6 hours after dosing OR 3) 7-11 hours after dosing. Every effort should be made to collect the PK samples at discrete time intervals during Visits 2, 3, 4, and 5. However, if the interval is the same across these visits, then the collection time should vary within that interval.
- g Participation in the effort to identify biomarkers is an optional component of the study requiring a separate informed consent.
- h The biomarker sample taken at the Week 12/EOT visit in the antecedent study is the Baseline sample for the present study.
- i The CGI-I assessments at Weeks 2, 12, 26, and 40/EOT will be a comparison with the baseline state of the illness in the present study (i.e., Visit 1 of ACP-2566-004).
- j Investigational product will be shipped directly to the subject. Confirmation of delivery to the subject will be made by a visiting nurse. Study drug shipment, return, and accountability will be performed in accordance with the drug distribution plan. In addition, study drug will be dispensed at the site during the Baseline visit when the visit is conducted in the clinic.
- k Subjects who roll over into the subsequent open-label study (ACP-2566-005) will not have the safety follow-up telephone call or telemedicine visit.
- l Study visits may be done off-site rather than in the clinic with the prior approval of the Sponsor or Medical Monitor. When a study visit takes place off-site, the physical examination will not be required. Weight should be measured whenever possible at off-site visits. Measurement of weight is necessary at Baseline in order to determine the starting dose. The RTT-COMC should be completed if possible, but it is not required.
- m Subjects for whom the Baseline visit of this study is not on the same day as the Week 12/EOT visit of the antecedent study will have blood drawn for Baseline values 3 to 14 days before the Baseline visit.

21.2 Summary of Version Changes

| Version No: | Document History Description of Update | Author(s) | Version Date |
|-------------|---|------------|------------------|
| 1.0 | Original version | [REDACTED] | 09 December 2020 |
| 2.0 | Added MECP2 Groupings; added definitions of RSBQ subscores; clarified analysis visit windowing | [REDACTED] | 21 April 2021 |
| 3.0 | Clarified text throughout. | [REDACTED] | 20 October 2021 |
